5.1.3 EAS Earhook Device

The earhook hardware shall consist of a canal receiver leveraged from commercially available Phonak Canal Receiver hearing instrument Technology (CRT) that is physically connected to and used in conjunction with a compatible Advanced Bionics (AB) prototype sound processor to provide both acoustic and electric stimulation to the same ear. Design changes incorporated

through the evaluation of an EAS earhook may address issues of sound preference, performance, reliability or cosmetics, and ease of use.

The types of changes anticipated to occur during development of the EAS Earhook are:

- Design modifications to molded materials (e.g. plastic, rubber, silicone or Teflon) to address cosmetic issues (e.g. mold flash or mold sink) or to incorporate suggested improvements.
- Substitution of one biocompatible material for another biocompatible material of a different grade with respect to particular mechanical properties (e.g. sheer strength, impact strength) to improve reliability, yields or cosmetics. *Note: The molded materials are known biocompatible materials for which Advanced Bionics has ISO 10993 test results on file.*

Figure 1 – EAS Earhook Mechanical Mockup

6.0 Study Objectives

The primary objective of the feasibility study is to evaluate whether *functional* low-frequency acoustic hearing sensitivity can be retained in newly implanted adults with partial deafness (considerable low frequency acoustic hearing profiles with severe-to-profound high frequency sensorineural hearing loss) following the implantation of the HiResolution™ 90K™ Advantage cochlear implant with the HiFocus™ Mid-Scala electrode to further support the development and completion of the Advanced Bionics electro-acoustic stimulation (EAS) technology. Functional hearing is defined as unaided acoustic hearing thresholds (in dB HL) sufficient to be aided with conventional amplification (≤ 80 dB HL). For purposes of this study, the specific criteria to be used is postoperative unaided low frequency audiometric thresholds in the treated ear up to 80 dB HL for at least one frequency from 125-1000 Hz.

There are two groups of study participants that will be recruited for the feasibility study to support the development of electro-acoustic stimulation technology for a partial deafness population: a newly implanted group and an existing implanted group. Each participant group will complete a 12 month test study endpoint visit. Each participant group will have the option to enroll in an EAS Extended Use Arm at the discretion of the managing clinician and the subject. The EAS Extended Use Arm is optional and will provide access to the investigational EAS device up until the point of full commercialization.

Assessment of each participant group (newly and existing implanted groups) will last a minimum of approximately 15-19 months, and will assess the level of residual acoustic hearing (by measurement of audiometric thresholds) and speech understanding performance in the treated ear (and bilateral listening condition) throughout the study.

Newly implanted study participants who demonstrate and meet the functional preservation of hearing post-implantation (by measurement of audiometric thresholds) at the one month post device activation visit at the participating study sites will be fit with the AB prototype EAS sound processor at his/her managing hearing care center. A more acute fitting postimplantation is beneficial to gain further understanding and insight in evaluating the effects and abilities of perceptual order with various arrays of inputs (acoustic and electric input to an auditory pathway), the time to integration and acclimatization assessed using various outcome measures.

Existing implanted study participants identified and recruited at the participating study centers will also be fit with the prototype EAS device at his/her managing hearing care center. The Sponsor believes it is important in an existing implanted group to also gain insight as to the integration of acoustic and electric frequency representation, sound quality and listening preference. Existing implanted study participants recruited for the study may have been implanted off label on their own accord or through another investigational study. Objective audiometric and speech recognition outcomes, in addition to subjective outcomes with the investigational external device system and components will be obtained at scheduled study test intervals at the participating study centers. Finally it is helpful to gain insight into fitting preferences and ease of use in software from hearing care specialists when simultaneously programming electric and acoustic stimulation in a partially deafened clinical population implanted with the Advanced Bionics System. The Sponsor intends to request feedback from the managing hearing care specialists from the participating centers throughout the study period to gain this insight.

All device-related and non-device-related adverse events will be tracked and reported accordingly through the 12 Months Post Initial Device Fitting Visit. Device-related or procedure-related adverse events will be reported throughout the EAS Extended Use Arm.

7.0 Study Protocol

7.1 Study Design and Justification

This study uses a prospective within-subjects repeated-measures design in which each subject serves as his/her own control. Single-subject repeated-measures study design is appropriate as it accommodates the heterogeneity that characterizes hearing-impaired populations. As it is not feasible to conceal the presence or absence of a cochlear implant from device recipients and/or clinical investigators a blinding procedure would not be an appropriate trial design for this feasibility study. Adverse events will be tracked and reported to the FDA according to the requirements of an IDE investigation until the study is closed. The AEs will be recorded and tracked between completion of the informed consent form (signed and dated) and two weeks after the participant's last study visit.

7.2 Study Endpoints

7.2.1 Efficacy :

The purpose of the proposed feasibility study is to evaluate and complete technology development for the combined sound delivery of electric and acoustic stimulation (EAS) to the treated ear. The collection of efficacy data to support product approval is not part of this feasibility study. However, as part of this feasibility, some audiometric, speech performance and subjective outcome data will be collected.

Specifically, for the newly implanted group: audiometric threshold measures at various, defined postoperative test intervals in the treated ear will be collected and compared to preimplant audiometric thresholds (using pure-tone average of .125, .25, .5 and 1kHz for comparison) . Measures of speech understanding and subjective outcomes will also be collected. Specifically,

collection of monosyllabic word recognition performance in quiet using the CNC word test and sentence recognition in noise using AzBio sentence test pre- to-post device activation will be compared for the newly implanted group. The Speech, Spatial Qualities (SSQ), Abbreviated Profile of Hearing Aid Benefit (APHAB), and Sponsor developed patient questionnaire(s) will be compared pre-to-post device activation to provide a subjective measure of patient perceived hearing performance/auditory benefit with this combined technology.

Audiometric, speech performance and subjective assessments will be additionally administered and evaluated for the existing implanted group participants enrolled in the feasibility study in an effort to gain insight with respect to EAS technology and postimplant performance. The Sponsor will make efforts to request preimplant hearing threshold data for the existing implanted group of participants in an attempt to evaluate and offer further insight as to the level of acoustic hearing preservation postimplantation with the Mid-Scala electrode array. These records for existing implanted participants may or may not be available to the managing clinical center and/or study Sponsor; however, the attempt at retrieval of this information will be made.

7.2.2 Safety

As part of this study, data (adverse event) will be collected and evaluated to ensure that the safety of patients is maintained accordingly as per requirements of an IDE and respective center Institutional Review Board guidelines for reporting.

7.3 Study Duration

The participant's study endpoint for the feasibility study is following completion of the twelve month test interval. It is expected that study participation for a subject enrolled in the feasibility study will involve a minimum 15-19 month commitment allowing for all scheduled test intervals and assessments.

The number of subjects proposed for recruitment in this feasibility study is estimated to be large enough to allow for trend analyses and to provide data suitable to support and complete product development.

7.4 General Subject Population

Projected total study enrollment under this feasibility study is 50 subjects. The Sponsor expects to add to current study recruitment and implant up to an additional 25 adult subjects across 20 study sites in the United States and recruit 15 existing implanted subjects with HiRes90K™ Advantage cochlear implant with HiFocus™ Mid-Scala electrode. The additional 25 subjects for the newly implanted group is additive to the original N=10 subjects (based on initial FDA study approval), thus 35 newly implanted subjects are to be recruited. The existing implanted group of subjects to recruit remains (N=15).

Prior to recruitment, written approval of the investigational plan and informed consent form will be obtained from the FDA and associated participating study center Institutional Review Boards (IRBs). Study participants are required to meet the study inclusion criteria (provided below) as determined by respective medical/hearing care providers. All consented participants meeting

criteria for the newly implanted group will be implanted with the commercially available HiResolution Bionic Ear Cochlear Implant System with the HiRes 90K™ Advantage implant with HiFocus™ Mid-Scala electrode and fit with a currently commercial ear-level (i.e. Naïda family) Advanced Bionics sound processor. A participant's ability to undergo the surgical procedure for cochlear implantation is determined respectively by the participant's managing medical/hearing care providers at his/her implant center. Existing implanted study participants recruited for the study may have been implanted off label on their own accord or through another investigational study.

7.5 Newly Implanted Group Inclusion and Exclusion Criteria

Inclusion criteria:

- Ability to provide informed consent
- No previous cochlear implant experience in either ear
- 18 years of age or older
- Up to a moderate sensorineural hearing loss in the low-to-mid frequencies (pure tone average ≤ 65 dB for 125, 250, 500, and 1000 Hz) and a severe-to-profound sensorineural hearing loss in the high frequencies (pure tone average ≥ 70 dB HL for 2,000, 3000, 4,000, and 8,000 Hz) in the ear to be implanted
- Aided CNC word recognition score up to 50% in ear to be implanted
- Up to a moderate sensorineural hearing loss in the low-to-mid frequencies (pure tone average ≤ 65 dB for 125, 250, 500, and 1000 Hz) and a severe-to-profound sensorineural hearing loss in the high frequencies (pure tone average ≥ 70 dB HL for 2,000, 3000, 4,000, and 8,000 Hz) in the contralateral (non-implanted) ear
- Aided CNC word recognition score up to 80% in the contralateral ear
- English language proficiency
- Willingness to use an ear-level sound processor postoperatively for the duration of the study trial
- Willingness to participate in all scheduled procedures outlined in the protocol

Exclusion Criteria:

- Preoperative audiometric conductive overlay of 15 dB or greater at two frequencies or more in range of 500-1000 Hz *in the ear to be implanted*
- Congenital hearing loss (for purpose of this study, onset prior to age 2 years*)
- Duration greater than 30 years of severe-to-profound high-frequency hearing loss
- Cochlear malformation or obstruction that would preclude full insertion of electrode array *in the ear to be implanted*
- Medical or psychological conditions that contraindicate surgery or impact the ability to manage an implanted device or the study related procedures as determined by the investigator
- Deafness due to central auditory lesion or cochlear nerve deficiency, diagnosis of auditory neuropathy/dys-synchrony *in either the ear to be implanted or the contralateral ear*
- Active middle-ear disease/infection *in the ear to be implanted*
- Unrealistic expectations regarding potential benefits, risks and limitations inherent to implant surgical procedures as determined by the investigator
- Unwillingness or inability of subject to comply with all investigational requirements as determined by the investigator

**Based on critical period for speech and language development*

EAS Fitting Inclusion Criteria: *Newly Implanted and Existing Implanted Groups*

- Ability to provide informed consent
- 18 years of age or older, *unilaterally implanted* with HiRes90K™ Advantage cochlear implant with HiFocus™ Mid-Scala electrode and fit with an ear-level sound processor (i.e. Naída family device)
- Postoperative unaided low frequency audiometric hearing thresholds in the treated ear up to 80 dB HL for at least one frequency from 125 – 1000 Hz
- English Language Proficiency
- Willingness to participate in all scheduled procedures outlined in the study protocol

EAS Fitting Exclusion Criteria:

- *Unilaterally implanted* with HiRes 90K™ Advantage cochlear implant with HiFocus™ Helix® and HiFocus™ 1j electrode
- Exclusive use of a body worn external sound processor
- Deafness due to central auditory lesion or cochlear nerve deficiency, diagnosis of auditory neuropathy/dys-synchrony *in either the implanted or the contralateral ear*
- Postoperative unaided low frequency audiometric hearing thresholds in the treated ear exceeding 80 dB HL at each frequency from 125 – 1000 Hz Unwillingness or inability of subject to comply with all investigational requirements as determined by the investigator

7.6 Participant Withdrawal

Study participants may withdraw from the study at any time, with or without reason, and without prejudice to further treatment. The study site investigator(s) and/or study Sponsor has the right to discontinue study participants. Participants can be discontinued for the following reasons:

- Voluntary withdrawal of consent made by the participant
- A safety concern identified by the Principal Investigator, the Sponsor, or any third party
- Failure to attend, provide required testing, feedback or documentation for a respective follow-up visit after three documented attempts to contact the subject

Participants who withdraw or who are discontinued from the study will be reported accordingly to the study Sponsor and the study center's Institutional Review Board in accordance to respective guidelines. If a subject was discontinued because of a device-related adverse event or serious adverse event (SAE), the subject must be followed until the serious adverse event is resolved, the point at which the subject withdraws HIPAA authorization, or the study is concluded.

The Investigator (or authorized delegate) in cooperation with the study monitor will complete a tracking log and/or enter into the electronic data capturing system the disposition of each enrolled subject (completed study, withdrew, discontinued).

8.0 Study Procedures

8.1 Recruitment

Participants who meet the study criteria will be recruited from hearing-impaired patient populations at the participating study sites. A participant's willingness and ability to meet the follow-up requirements will be determined by the investigator and informed consent will be obtained. A signed and dated informed consent will be kept in the participant's study record at the study site and copy provided to the participant accordingly. Study participants must also sign a release that authorizes access of medical records to the study sponsor, investigators, monitors and the FDA prior to proceeding with screening assessments. This release may be its own signature line contained within the Informed Consent Form (see Exhibit 2, Attachment 2.3, Appendix C for template) or may be a separate authorization, consistent with institutional policy.

8.2 Participant Screening

No investigational procedures are used to screen patients for study eligibility. Subjects eligible to participate in this study will be evaluated to determine if they meet the inclusion requirements for the study. Informed consent will be obtained before any study-specific tests or procedures are conducted. An individual is considered to be enrolled as a study participant only after the informed consent document has been signed and dated. Each subject will be assigned a unique identifier at the time of enrollment.

8.3 Test Measures

Primary Test Measures Used in Feasibility:

For the newly implanted group: the CNC monosyllabic word test will be used as the primary test metric for determination of preimplant candidacy. In addition to the primary metric, AzBio Sentences in Noise will be administered preoperatively for the ear to be treated (implanted) and in a bilateral listening condition. Postoperatively, for both the enrolled newly implant group and the existing implant participant group, CNC words in quiet and AzBio Sentences in Noise will be evaluated for both the treated ear and in the participant's bilateral listening condition.

In order to isolate the *treated ear* during testing (conditions specified), a foam earplug and an over-the-head earmuff will be used in the contralateral (non-treated ear). This method will be referred to in the remainder of this document as 'plug and muff.'

8.3.1 Audiometric Measures:

Unaided air and bone conduction hearing thresholds (in dB HL) will be measured for each ear using the standard audiometric technique for pure-tone air and bone-conduction testing (refer to Exhibit 2, Attachment 2.3, Appendix A for the speech testing guidelines). Given the clinical population for which this feasibility study is evaluating (partial deafness), standard audiometric clinical masking procedures are applied as necessary to reduce any potential contribution of the better hearing ear during pre and postimplant assessments.

- Tympanometry (226 Hz)
- Unaided air conduction thresholds using insert earphones at octave and inter-octave frequencies will be obtained (125, 250, 500, 750, 1000, 1500, 2000, 3000, 4000, 6000 and 8000 Hz)
- Unaided bone-conduction hearing thresholds for the frequencies 250, 500, 1000, 2000, 3000 and 4000 Hz will be measured
- Aided warble-tone soundfield testing for the frequencies 250, 500, 750, 1000, 1500, 2000, 3000, 4000 and 6000 Hz

Note: Clinician will need to confirm the study participant's response to any pure tone stimulus presented at 125 and 250 Hz as auditory "heard" versus vibrotactile "felt" and record the response accordingly. Postoperatively, if no measurable hearing at the limits of the test equipment is documented at 2 consecutive visits, unaided audiometric testing for the TREATED ear does not need to be completed.

[figure not shown]
8.3.2 Speech Perception Measures:

General speech perception testing procedures

All speech perception testing will be conducted using recorded stimuli presented from a single loudspeaker in at a minimum a single-walled sound booth capable of accommodating a calibrated, 90 degree speaker orientation. Audiometers will conform to ANSI standards for pure-tone and speech audiometry (ANSI) and/or Manufacturer Specifications.

Speech perception measures in soundfield are to be administered via a loudspeaker at 0° azimuth at a distance of one meter from the subject. Speech signals will be presented at 60 dBA. Speech levels will be calibrated to 60 dB SPL using a microphone placed at the approximate position of the subject's head (one meter from loudspeaker). Preoperatively, participants are tested in the defined 'aided' conditions using his/her hearing aid devices even if conventional amplification provides no added benefit over his/her acoustic hearing. Postoperatively, participants are tested in his/her preferred listening program (cochlear implant sound processor program) and in his/her everyday listening condition.

Speech stimuli may be delivered via an audiometer with a CD or MP3 player or by proprietary software developed by Advanced Bionics called ListPlayer.

Audiometric and speech perception testing at post device activation intervals is to be conducted prior to any device (i.e. cochlear implant sound processor, hearing aid, EAS sound processor) adjustment and/or optimization of program parameters. It is recommended that a listening check of the participant's device and confirmation of sufficient battery life be verified prior to testing at each study interval.

The study participant's commercial ear-level (i.e. Naída family) Advanced Bionics cochlear implant sound processor (which provides electric only stimulation) should be checked routinely and adjusted if necessary as done clinically at each scheduled test visit. Participants that qualify and are fit with an AB prototype EAS sound processor at the defined test interval outlined within the study protocol (EAS fitting visit); will use and be tested wearing this device for the remaining scheduled postoperative test intervals that are outlined accordingly within the investigational plan. Should the participant's residual acoustic hearing in the implanted (treated) ear decrease to a level outside the EAS fitting inclusion criteria during the 12 month test interval, he/she should resume use of his/her commercial (owned) Advanced Bionics cochlear implant sound processor and the AB EAS device be returned to his/her managing hearing care center.

In the event that study participants qualifying and using the EAS sound processor device experiences any issue (i.e. requires replacement and/or exchange) during the clinical study; the participant should resume use of his/her owned cochlear implant sound processor device so that the participant is never without sound until a replacement EAS device is received from Advanced Bionics. Should the participant experience an issue with the EAS study device in and/or around a scheduled study test visit; the test interval should be rescheduled within a two-week period from the originally scheduled date to allow time for a replacement EAS device to be sent to the participant. This is recommended in an effort to maintain consistency in study testing at scheduled intervals with study participants.

Consonant-Nucleus-Consonant (CNC) Word Recognition Test

The CNC monosyllabic word test (Peterson and Lehiste, 1962) is a validated test of open-set word recognition ability. The test will be administered in quiet at 60 dBA (target 0° azimuth) and scored as total number of words correct which will be expressed for results/reporting as percentage correct.

AzBio Sentence Test

The AzBio Sentence Test (Spahr and Dorman, 2005) is a validated test of open-set sentence recognition ability. The test will be administered in noise (target and noise 0° azimuth) at 60 dBA + 5 dB SNR using Speech-spectrum Noise (SSN) and scored as total number of words correct which will be expressed for results/reporting as percentage correct. The sentence tokens include both male and female speakers.

8.3.3 Patient Questionnaire:

Speech, Spatial and Sound Qualities Questionnaire (SSQ)

The SSQ (Gatehouse and Noble, 2004; Noble and Gatehouse 2006) will be used as a subjective, self-reported assessment of hearing status and hearing capability in everyday life prior to and during the feasibility study. The questionnaire is designed to measure self-reported auditory disability across a wide variety of domains to include: hearing speech in a variety of competing contexts; directional, distance and movement components of spatial hearing; segregation of sounds and attending to simultaneous speech streams; ease of listening; naturalness; clarity and identifiability of different speakers and music. The current standard versions of SSQ (5.6) and SSQ-B (5.6) will be used in the study.

Abbreviated Profile of Hearing Aid Benefit (APHAB)

The APHAB (Cox and Alexander, 1995) will be used as a subjective, self-reported assessment of hearing status and hearing capability in everyday life. The questionnaire will be administered pre and post-treatment to participants. APHAB is designed to measure self-reported auditory / communicative disability in various everyday situations. There are four subscales that are evaluated within the APHAB questionnaire: Ease of Communication (EC) the strain of communicating under relatively favorable conditions; Reverberation (RV) Communication in reverberant rooms such as classrooms; Background Noise (BN) communication in settings with high background noise levels and Aversiveness (AV) the unpleasantness of environmental sounds.

8.3.4 Additional Test Measures:

Sponsor-developed patient questionnaires apart from the SSQ and APHAB listed above may be used with study participants at different points throughout the study. Questionnaires and/or patient report scales related to Speech, Music Perception, Sound Quality or Device Usability, for example, may be additionally administered to participants during the feasibility study at various test intervals. Sponsor developed questionnaires and/or feedback may be obtained from the participating study centers related to hardware, software, programmability or device usability during the study.

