10.0 Statistical Methods

General Considerations

Individual outcomes will be compared across pre- and postoperative test conditions for audiometric and speech performance outcomes. No formal statistical hypothesis will be tested. At a minimum, individual data/outcomes will be tabulated and summarized for audiometric and speech performance outcomes to establish numbers of subjects showing improvement, no change or decrease in performance. Descriptive statistics may consist of counts, means, median and standard deviations, percent and relative frequency for categorical variables (i.e. questionnaire). The proposed sample size the Sponsor is aiming to recruit for participation of 50 total subjects is deemed sufficient for determining the feasibility for the development of electric and acoustic stimulation technology.

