11.0 Efficacy Measures

An objective of the feasibility study is to facilitate and complete development of a combined input acoustic and electric stimulation (sound delivery) technology. Collection of efficacy data to support product approval is not part of this feasibility study. As such, no formal statistical hypothesis is being posed and/or applied. As part of this feasibility study, the following data will be collected and evaluated:

1. Postimplant audiometric hearing thresholds will be compared to preimplant thresholds in the newly implanted group to assess preservation of any low frequency acoustic residual hearing in the treated ear post intervention with the HiRes 90K™ Advantage cochlear implant with the HiFocus™ Mid-Scala electrode. Specifically, unaided pure tone hearing threshold measurement in the treated ear compared to preimplant audiometric thresholds (using a pure-tone average of .125, .25, .5 and 1 kHz for comparison) will be assessed. Individual and group comparisons will be made. Results will be tabulated and summarized based on pre- to postoperative change in pure-tone average (PTA).
2. Additionally, monosyllabic word recognition performance in quiet for the treated ear using the CNC word test and sentence recognition in noise using AzBio sentence test pre-to-post device activation will be compared, tabulated and summarized for the newly

implanted group. AzBio sentence understanding in noise pre-to-postoperatively will also be compared, tabulated and summarized in the bilateral listening condition. The intent of this individual and group comparison is to address the contribution and benefit of the implant treatment option in a partial deafness population as compared to the preimplant listening condition.

3. The Speech, Spatial Qualities (SSQ) and the Abbreviated Profile of Hearing Aid Benefit (APHAB) questionnaire score comparison pre-to-post device activation will be conducted (in the newly implanted group) to provide a subjective measure of patient perceived hearing performance/auditory benefit with this combined technology. The SSQ and APHAB will aid in providing a measure of subjective perceived benefit; individual and group comparisons will be made. Additional subjective data collected (i.e. Sponsor developed questionnaires) in the feasibility study will also be tabulated and summarized to evaluate amount of improvement, no change or decrement.

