12.0 Safety Measures

12.1 Adverse Event Reporting

An adverse event (AE) is defined as any undesirable clinical occurrence experienced by a study subject when using the HiResolution System or when undergoing research procedures, whether or not the AE is considered to be device-related. The definition of an AE also includes any event related to any study procedures or to any underlying medical condition present at baseline that increases in severity during the study. An underlying medical condition that was present at the time of enrollment will not be reported as an AE, but any increase in severity during the study will be reported as an AE. The AEs will be recorded and tracked between the completion of the informed consent form and two weeks after the subject's last follow-up visit. During the EAS Extended Use Arm, reporting shall be limited to those AEs deemed device-related or procedure-related by the Investigator per the records requirements of 21 CFR 812.140(a)(3)(ii).

The following risks are identified as anticipated Adverse Events:

- Newly Implanted Group
 - Risks specific to this study
 - Possible loss of all residual hearing in the ear to be implanted, which may be permanent
 - Any Newly Implanted study participant experiencing a shift in audiometric threshold of 50 dB or greater at 2 or more test frequencies from 125-1000 Hz will be reported as an anticipated Serious Adverse Event under this feasibility study. Given the postoperative audiometric hearing threshold fluctuations expected after cochlear implantation (i.e. potential middle ear

fluid postop); the Serious Adverse Event reporting as defined will be reported at the 3 month postoperative test interval, a point at which things such as confounding middle ear involvement may resolve.

- Loss of all residual hearing may result in added difficulty hearing in various everyday listening situations. For example, locating the direction of a sound in the environment, perception of music may be altered or degraded, hearing your own voice or in the detection of sounds such as a door-knock or telephone ring.
- General risks
 - General anesthesia
 - Postoperative pain
 - Bleeding or infection
 - Possibility of damage to the facial nerve
 - Balance related issues (i.e. dizziness, vertigo)
 - Numbness
 - Swelling or discomfort around the ear
 - Taste disturbance
 - Increased ringing in the ears (tinnitus)
 - Neck pain
 - Skin reaction

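### The waiver of treated-ear audiometry can start before the 3-month hearing SAE check, leaving the worst ears without a current threshold

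*Combined protocol and SAP*

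**What the plan says.** Section 8.3.1 attaches a note to postoperative audiometry: once an absence of measurable hearing at the equipment limits is "documented at 2 consecutive visits, unaided audiometric testing for the TREATED ear does not need to be completed". It names no earliest visit at which this may apply.

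Section 12.1 defines a study-specific SAE for the newly implanted group: a shift of at least 50 dB at two or more frequencies between 125 and 1000 Hz. It adds that "the Serious Adverse Event reporting as defined will be reported at the 3 month postoperative test interval", and explains that early thresholds fluctuate, for example with middle-ear fluid, which may have cleared by then.

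Section 11.0 compares treated-ear PTA (0.125, 0.25, 0.5 and 1 kHz) before and after implantation, for individuals and for the group. Section 10.0 asks for individual outcomes to be tabulated "to establish numbers of subjects showing improvement, no change or decrease in performance", and states that "No formal statistical hypothesis will be tested". The primary objective in section 6.0 is whether functional low-frequency hearing survives implantation, judged by a threshold of 80 dB HL or better at one or more frequencies from 125 to 1000 Hz.

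Section 9.1 and Table 2 list unaided testing of each ear at 3, 6 and 12 months and do not mention the waiver. The supplied text does not say how a no-response is coded, how a waived visit is tabulated, or which denominator applies.

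**The concern.** Only an ear with no measurable response can qualify for the waiver, so whether a later threshold exists depends on the outcome itself. The waiver can also rest on readings that section 12.1 treats as too early for judging lasting loss.

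Two outputs are exposed. The 3-month SAE determination may have no 3-month audiogram in the participants most likely to meet the criterion, and the plan does not say which audiogram decides in that case. The PTA change at 3, 6 and 12 months may lack values for the same ears. Descriptive summaries are the only output of this study, and section 4.0 expects them to help set endpoints for a pivotal study, so an error here would be passed on.

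**Working it through.** **Timing (all inputs from sections 8.3.1, 9.1 and 12.1)**

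- First postoperative audiogram: initial fitting, 3 to 6 weeks after surgery. Second: 7 to 10 days later.
- Earliest second no-response: 21 + 7 = 28 days = 4.0 weeks after surgery. Latest for this pair of visits: 42 + 10 = 52 days = 7.4 weeks.
- 3-month visit: 84 ± 14 days after fitting, that is day 70 to 98. Counted from surgery: 21 + 70 = 91 days (13 weeks) to 42 + 98 = 140 days (20 weeks).
- The waiver can therefore precede the SAE interval. It can cover the 1-, 3-, 6- and 12-month treated-ear tests. Ears that fail the EAS fitting criterion have no 2-month visit.

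**What happens if waived ears are dropped**

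The plan gives no expected shift, SD or loss rate, so there is no figure of its own to reproduce. The only document input below is N = 35 (section 7.4: "thus 35 newly implanted subjects are to be recruited"). The rest are assumptions: k waived ears; tested ears shift by 10 to 20 dB on average; waived ears by 35 to 60 dB; 3 tested ears lack functional hearing. For the SAE columns, the extreme case is assumed, in which every waived ear meets the rule and no tested ear does.

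- Understatement of mean shift = (k/35) × (shift in waived ears − shift in tested ears). The gap runs from 35 − 20 = 15 dB to 60 − 10 = 50 dB.
- Retention if dropped = (35 − k − 3)/(35 − k). If kept = (35 − k − 3)/35.

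| k | Mean shift understated by | Retention, dropped | Retention, kept | SAE, dropped | SAE, kept |
|---|---|---|---|---|---|
| 2 | 0.9–2.9 dB | 30/33 = 90.9% | 30/35 = 85.7% | 0% | 2/35 = 5.7% |
| 4 | 1.7–5.7 dB | 28/31 = 90.3% | 28/35 = 80.0% | 0% | 4/35 = 11.4% |
| 7 | 3.0–10.0 dB | 25/28 = 89.3% | 25/35 = 71.4% | 0% | 7/35 = 20.0% |
| 11 | 4.7–15.7 dB | 21/24 = 87.5% | 21/35 = 60.0% | 0% | 11/35 = 31.4% |

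**What happens if early no-responses are carried forward without retest**

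The error then runs the other way. Each ear that would have regained functional hearing is still counted as lost, which lowers retention by 1/35 = 2.9 percentage points per ear.

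**A no-response is a censored value**

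The largest shift that can be recorded is the equipment limit minus the baseline threshold. The documents give no equipment limits. Assuming limits of 80 to 120 dB HL and a baseline threshold of 65 dB (the ceiling for low-frequency PTA at entry), the recordable shift is 80 − 65 = 15 dB to 120 − 65 = 55 dB. Even a tested total loss may not compute as 50 dB unless the plan says how a no-response counts.

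**The case against.** A reader might infer that the waiver removes the worst outcomes and that preservation will look better than it is. The documents do not support that.

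- Testing becomes optional; it is not barred. No passage drops a waived participant.
- Each waived ear has two recorded no-responses, so it can be tabulated as a decrease. Provided the equipment limits reach 80 dB HL, it is also a known failure of the functional criterion at its last test.
- Section 9.1 keeps all newly implanted participants in the 3-, 6- and 12-month visits whether or not they qualify for EAS.
- The SAE rule covers every newly implanted participant. Loss of all residual hearing is separately listed as an anticipated adverse event, and permanent impairment of a body function counts as serious. The text does not say that a missing 3-month audiogram means no event.
- Bone conduction and tympanometry are scheduled at fitting and at 1 week. If absence of measurable hearing is read to include bone conduction, a purely conductive early loss might not trigger the waiver.
- Appendices A and B and a figure next to the waiver note are not in the supplied text; a no-response code may be there.
- The study is descriptive, and its data are not meant to support approval.

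These points stand. They rule out a certain direction of bias and any claim that exclusion is prescribed. They leave the timing conflict in place. Two early no-responses permit the 3-month audiogram to be skipped, although the plan chose that interval because earlier readings are unreliable. Permanent impairment is also hard to establish without a later threshold.

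**Conclusion.** The concern holds as a conflict between the waiver in section 8.3.1 and the 3-month SAE timing in section 12.1, together with an unstated treatment of waived visits. The timing follows from the plan's own visit windows and needs no assumption.

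The direction and size of any bias are conditional. If waived visits are treated as missing, preservation is overstated, by roughly 1 to 16 dB in mean shift over the assumed inputs. If early no-responses are carried forward untested, lasting loss may be overstated. If no-responses are kept and remain true, the bias is zero. The number of waived ears, the shifts and the equipment limits are not in the documents, so the figures above are illustrations and not estimates.

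No test, alpha or power is affected. The point should be fixed, but it does not stand in the way of running the study.

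**What to change.** Reconcile section 8.3.1 with section 9.1, Table 2 and section 12.1 so that the waiver cannot take effect until the 3-month treated-ear audiogram has been obtained. That test is already scheduled for each ear, so the cost is a few minutes of testing in the few participants affected.

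For visits waived after that, add to section 11.0 that:

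- the visit is tabulated as a documented no-response;
- the participant stays in a denominator of all implanted subjects;
- the number with no response is reported, with median PTA change beside any mean.

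State also how a no-response counts towards the 50 dB criterion. Medians and counts are already among the descriptive statistics allowed by section 10.0, so this needs only a few sentences.
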